**B] Allocation concealment mechanism:**

The supervisor of the study ([name]) will write the randomization numbers of the patients on opaque white papers folded three times to form sealed envelopes and store it inside a box. The codes for randomization will be securely held at the secretary's office.

**C] Implementation:**

At the time of intervention, the main operator will send the patient to the secretary's office. Then, the assigned employee will open the box and ask the patient to select one envelope. The main operator will assign each participant for the corresponding intervention either (friction or frictionless group) according to the list of codes of randomization.

Assignment to either intervention will occur before levelling and alignment stage.

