## C] Interventions:

➤ **Medical History Questionnaire:**

For every patient, to exclude the presence of any systemic condition interfering with orthodontic treatment.

➤ **Clinical Examination:**

Oral structures will be examined to identify caries, fracture or missing teeth. Gingival tissues will be carefully examined for any gingivitis, periodontitis, recession, or lesions.

> **Diagnosis**

Check the potential patient to fulfill the previously mentioned inclusion criteria. Every participant will be asked to sign an informed consent about the study. Full set of records (study models, panorama radiograph and lateral cephalometric radiographs, photos) will be taken for every patient as part of the routine procedure for treatment of patients in the clinic of the Orthodontics and Dentofacial Orthopedics Department, Future University in Egypt.

> **Clinical Procedure:**

After taking pre-treatment records, every patient will receive:

- Bonding of all teeth except for first premolars and banding/bonding the first and second molars will be done using Roth prescription brackets (0.022 x 0.028 slot)\*.
- Miniscrews will then be placed in the upper arch between the second premolar and first molar\*\*.
- The patient will be referred for extraction of first premolars.
- Anchorage will be secured, followed by Leveling and alignment for the bonded and banded teeth through following the wire sequence: 0.014 Nitti, 0.016×0.022 Nitti and 0.017×0.025 StSt.

- After levelling and aligning is completed (right before retraction), the patient will be referred for the uptake of pre-intervention records:
  - a- CBCT
  - b- Impression and models
  - c- photo (Extraoral & Intraoral)
  - d- pain questionnaire

➢ **Acquisition of pre-intervention records:**

- The patient will be referred for the uptake of a CBCT, which are considered to be the T0 records.
- Impressions will be taken before retraction (without the archwire in place) followed by digital scanning of produced models.
- Photos (Extraoral & Intraoral)
- Pain questionnaire distributed with explanatory session on it

➢ **Beginning of Retraction:**

*Frictionless group:*

- A braided ligature wire extended between the second premolars and miniscrews will be used for proper indirect anchorage control.
- Closing retraction T-loops will be fabricated using 0.017 x 0.025 TMA wire. The loop will be positioned halfway the extraction space and the canine. [40,41].
- A gable angle of 45° will be added to the posterior segment.

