***Friction group:***

- Crimpable hooks added to the arch wire (0.017"x0.025" Stainless steel) distal to the lateral incisor passing near the center of resistance of the anterior segment.
- A ligature wire extending between the second premolar and miniscrews will be used for proper anchorage control.
- Retraction will start on a 0.017"x0.025" Stainless steel wire using elastomeric chain (force applied will be 200 g per side) [43] extending between the crimpable hooks and the miniscrews.
- The force will be measured by a force gauge and reactivated every 4 weeks maintaining constant force of retraction all over the retraction phase.

➢ **Follow up visits**

Patients will be asked to attend for follow up sessions every 4 weeks for:

- Evaluation miniscrews stability.
- Replacement of the power chain to maintain a force of 200 gm per side.
- Reactivation of the T-loop by further distal activation and cinch back.
- Impression taking to determine the anchorage loss

➤ **Criteria for discontinuing or modifying the allocated intervention:**

In cases of prolonged swelling or pain related to the miniscrews, the patient will be given strict oral hygiene measures and may wait for three weeks before the beginning of retraction.

In cases of loose or broken miniscrews, the screw will be removed and replace the miniscrew after total resolution of the inflammation.

➤ **Criteria for Ending the retraction:**

a-class I canines

b-normal overjet

c- closure of extraction space

d- reaching good profile

Ø **Post-retraction Questionnaire:**

The patients of both groups will be asked to fill in questionnaires regarding their experience with their allocated technique during the whole retraction period from day of extraction till the end of retraction.

Ø **Retraction records**

Following “En-masse retraction”, patients will be referred to the same radiology center to acquire the final cone-beam CT to assess the movement and inclination of anterior teeth.

The final dental model will be used to assess the rate of retraction and molar anchorage loss achieved throughout the study.

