## **E] Participant timeline:**

1. The principle investigator will screen the potential patients through careful clinical examination of patients at the Orthodontics and Dentofacial Orthopedics department, Faculty of Oral and Dental Medicine, Future University in Egypt.
2. All recruited patients should fulfill the previously mentioned inclusion and exclusion criteria.
3. Every participant will be asked to sign an informed consent before the beginning of the study.
4. Pre-intervention records will be taken for each participant after enrollment to ensure proper diagnosis.
5. The principle investigator will randomly allocate the patients to one of the intervention groups.
6. Anchorage will be secured by placement of miniscrew, followed by extraction of the first premolar.
7. Active intervention will begin after proper levelling and alignment of teeth through following the wire sequence: 0.014 NiTi, 0.016×0.022 NiTi and 0.017×0.025 StSt.
8. The principle investigator will take pre-retraction records for every participant T0.
9. In Friction mechanics group, Power chain is used for anterior segment retraction while in Frictionless group, T-loop is used for retraction.
10. Each patient will come every 4 weeks for follow up visit, for appliance activation and uptake of impression for interim records.
11. After complete space closure, the principle investigator will take post-retraction records for each participant T1.

- 12.Every patient will fill up a questionnaire regarding his experience during treatment.
- 13.The principle investigator will continue the normal treatment and achieve proper finishing for every patient after the end of the study.

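### Patients are randomised before miniscrews, extraction and levelling, although the arms differ only from retraction onwards; drawing the envelope after T0 would avoid randomised patients with no outcome, at low cost and for a small gain

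*Protocol*

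**What the plan says.** Under Assignment of interventions, Implementation, the Protocol fixes the draw: "Assignment to either intervention will occur before levelling and alignment stage". The same section opens differently: "At the time of intervention, the main operator will send the patient to the secretary's office".

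The Participant timeline gives the order. Step 5 reads "The principle investigator will randomly allocate the patients to one of the intervention groups". Step 6 is miniscrew placement and extraction. Step 7 says "Active intervention will begin after proper levelling and alignment of teeth", and step 8 says "The principle investigator will take pre-retraction records for every participant T0".

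Under Interventions, bonding, miniscrews, extraction and levelling are listed once, for all patients. T0 follows: "After levelling and aligning is completed (right before retraction), the patient will be referred for the uptake of pre-intervention records". The T0 items include "Pain questionnaire distributed with explanatory session on it". Separate instructions for the two groups first appear under Beginning of Retraction.

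The Outcomes section defines all outcomes as the difference between T0, at the start of retraction, and T1, after space closure. The Blinding section says operators cannot be blinded and that only the outcome assessors are. The post-retraction questionnaire asks patients about "their experience with their allocated technique during the whole retraction period from day of extraction till the end of retraction".

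**The concern.** No step between allocation and T0 uses the allocation, yet the arm is already known during that time. This has three consequences.

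- A patient lost during the common phase counts as a post-randomisation loss. Without a T0 record, no T0–T1 outcome can be calculated for that patient, whatever the analysis.
- The operator who decides when a patient is ready for T0 knows the arm, and patients may know it too. If losses before T0 depend on that knowledge, the patients who reach T0 may differ between arms. Blinded reading of scans and models does not address this.
- The wording does not fit together. Implementation opens by placing the draw at the time of intervention and closes by placing it before levelling, while timeline step 7 starts active intervention after levelling. The questionnaire asks about the allocated technique from the day of extraction, when neither technique is yet in use.

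At stake are avoidable missing outcomes and a slight possible shift in the comparison of anchorage loss.

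**Working it through.** **Order of events**

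| Event | Timeline step | Does care differ by arm? |
|---|---|---|
| Allocation | 5 | – |
| Miniscrews, extraction | 6 | No |
| Levelling and alignment | 7 | No |
| T0 records | 8 | No |
| Retraction | 9 | Yes, for the first time |
| T1 records | 11 | Outcome = T1 − T0 |

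Allocation could be drawn between steps 8 and 9 without changing any earlier step.

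**The plan's own sample size.** Inputs from Sample size calculation: difference 1.0, SD 0.76 (no unit given; taken as mm), alpha 0.05 (taken as two-sided), power 0.80.

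n per group = 2 × (1.96 + 0.84)² × 0.76² / 1.0² ≈ 9.1, so 10, as stated. The exact t-test power at 10 per group is 0.795. Going from 10 to 15 allows a total loss of 1 − 10/15 = 33%.

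**Power if patients are lost before T0** (noncentral t, same inputs):

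| Patients per arm | Power |
|---|---|
| 15 v 15 | 0.935 |
| 14 v 14 | 0.918 |
| 13 v 13 | 0.896 |
| 12 v 12 | 0.869 |

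Power is therefore not the main issue.

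**Shift if the losses are selective.** The documents give no loss rate for levelling, so k = 1, 2 or 3 of 15 per arm (7% to 20%) is assumed. In one arm the k patients with the highest leaving score go, and that score has correlation r with later anchorage loss. In the other arm k leave at random. There is no treatment effect. With S the expected sum of the k largest of 15 standard normal values (1.736, 1.248 and 0.948 for the top three):

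shift in the arm mean = −r × 0.76 × S / (15 − k)

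- k = 1, r = 0.3: −0.3 × 0.76 × 1.736 / 14 = −0.028
- k = 2, r = 0.3: −0.3 × 0.76 × 2.984 / 13 = −0.052
- k = 3, r = 0.5: −0.5 × 0.76 × 3.932 / 12 = −0.125

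Simulation of the same setting (400,000 trials each, unpaired t-test at 0.05, Monte Carlo standard error about 0.04 points) gives these false-positive rates, with the size of the shift in brackets:

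| k of 15 | r = 0 | r = 0.3 | r = 0.5 | r = 1 (upper bound) |
|---|---|---|---|---|
| 1 | 5.0% | 5.1% (0.03 mm) | 5.5% (0.05 mm) | 7.2% |
| 2 | 5.0% | 5.4% (0.05 mm) | 6.2% (0.09 mm) | 10.7% |
| 3 | 5.0% | 5.7% (0.07 mm) | 7.2% (0.12 mm) | 15.4% |

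Repeat runs differ by about 0.1 point.

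**A second route to the size.** Bias = (difference in loss between arms) × (mean outcome of lost minus retained patients). A 10-point difference in loss and 0.5 SD give 0.10 × 0.5 × 0.76 = 0.04. A 20-point difference and 1 SD give 0.20 × 1 × 0.76 = 0.15. Both are small against 1.0.

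**Price of a later draw**

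- Enrolment to randomise 30: 30 / (14/15) = 32.1, so 33; 30 / (13/15) = 34.6, so 35; 30 / (12/15) = 37.5, so 38. At 5% and 10% loss: 30 / 0.95 = 31.6, so 32; 30 / 0.90 = 33.3, so 34.
- With enrolment held at 30, the same losses leave 28, 26 or 24 randomised and some envelopes undrawn. With 24 of 30 drawn, P(9:15 either way) = 2 × 5005 / 593775 = 1.7% and P(10:14 either way) = 2 × 45045 / 593775 = 15.2%, together 16.9%. Power is 0.859 at 10 v 14 and 0.847 at 9 v 15.
- Power averaged over the possible splits is 0.917, 0.894 and 0.866 for 28, 26 and 24 patients, the same as for early allocation with 2, 4 or 6 random losses.

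**The case against.** The strongest reply is that this is a preference rather than an error. The draw is concealed, its time is stated, and step 5 agrees with the closing sentence of Implementation. Because care is common until retraction, losses before T0 can differ systematically between arms only through knowledge of the arm, and nothing in the Protocol shows that patients leave for that reason. The one-sided loss and the correlation in the calculation are assumptions. The allowance from 10 to 15 per group absorbs moderate loss, and at fixed enrolment a later draw gains no power. The operator remains unblinded during retraction. The change also touches the questionnaire period, and the list is built on patient numbers.

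Much of this stands. Early allocation is legitimate, the effect is small, no power gain can be claimed at fixed enrolment, and operator knowledge during retraction is untouched. *Intervention* is also used loosely elsewhere in the Protocol, so the wording conflict is mild.

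Three points remain. The allowance of 15 protects power, not comparability if losses depend on the arm. Such losses are conceivable on the Protocol's own account: patients are not blinded, and the rationale notes that some may find loops uncomfortable. The questionnaire is already handed out at T0, and the 30 coded envelopes can be drawn then just as well.

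**Conclusion.** The concern holds as a recommended design improvement, not as a flaw that invalidates the trial. The draw comes earlier than the design needs, and patients lost before T0 become randomised patients without an outcome.

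Under the assumed 1 to 3 selective losses of 15 and a correlation of 0.3 to 0.5, the shift is 0.03 to 0.12 mm against a planned 1.0, and the false-positive rate is about 5.1% to 7.2%. It stays at 5% if losses are random. These figures rest on an assumed loss rate, one-sided selection, an SD of 0.76 in mm and an unpaired t-test.

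A later draw removes only the part that arises before T0. It raises power only if lost patients are replaced, which the recruitment rule of screening until the number is reached allows.

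**What to change.** Change these places together.

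- **Implementation, opening sentence:** replace the reference to the time of intervention with: *After the T0 records are taken and immediately before retraction.*
- **Implementation, last sentence:** replace with: *The concealed envelope will be drawn once levelling and alignment is complete and the T0 records are taken, immediately before retraction. Patients who leave earlier will be reported as enrolled but not randomised.*
- **Participant timeline:** move step 5 to directly after step 8 and renumber.
- **Post-retraction Questionnaire:** limit the period to the start till the end of retraction. Add: *Experience between extraction and T0 will be recorded at T0, before allocation, and reported as pre-randomisation.*
- **Secondary outcomes, Pain:** make the period match: during retraction, with extraction to T0 recorded separately at T0.

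The waiting rule for miniscrew problems stays as written; where it is used, the envelope is drawn after the wait.

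**Cost.** The list, envelopes and visits stay the same. The Protocol should state whether the target of 30 counts enrolled or randomised patients. If randomised, 33 to 38 must be enrolled at the assumed 7% to 20% loss (32 to 34 at 5% to 10%), so more patients go through the common phase. If enrolled, 24 to 28 are randomised and the arms may be unequal. Even 24 leaves room for 4 later losses (4/24 = 17%) before the total falls to the 20 that the sample size section requires.

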**D] Blinding:**

**Blinding of the operators:** Blinding will not be possible for the operators during the application interventions and during the follow up visits. The principal operator is responsible for assigning subjects to interventions according to the concealed allocation, appliance activation at follow up visits, dental impressions and acquisition of dental casts.

**Blinding of the outcome assessors:** It is a single blinded study, therefore, only the outcome assessors will be blind. The patients name will be sealed from pre and post radiographs and study models. Then two assessors will carry out, blindly and Independently, the measurements and analysis of the study.

### **III) Data collection, management and analysis:**

#### **A] Data collection methods:**

##### ***Primary outcomes:***

**1. Anchorage loss:** will be accessed by the principal investigator via CBCT taken before and after the completion of retraction by identifying the landmarks, reference lines and planes, then will interpret the measurements in degrees and millimeters.

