##### ***Secondary outcomes:***

**1. Retraction rate:** to assess the antero-posterior movement of anterior teeth and first molars, the principle investigator will take study models for every participant monthly during the follow up visits. Then will digitize the models and identify the landmarks, reference lines and planes on the pre, interim and post-retraction digital dental models for measurements reading. Also, by identifying the landmarks, reference lines and planes using CBCT taken before and after the completion of retraction.

**2. Pain:** each patient will fill a questionnaire regarding his treatment experience in a Visual Analog Scale (VAS) scoring from 1-10 by making a handwritten mark on a 10-cm line that represents a continuum between “no pain” on the left end (0 cm) of the scale and the “worst pain” on the right end of the scale (10 cm). The questionnaire will include several questions related to oral hygiene, pain and discomfort experienced throughout the trial.

**3. Root resorption:** will be accessed by the principle investigator via CBCT taken before and after the completion of retraction. The resorption will be identified using

scoring system of Levander and Malmgren that classifies it into 5 grades: 0, no root resorption; 1, mild resorption, with the root of normal length and only an irregular contour; 2, moderate resorption, with small areas of root loss and the apex having an almost straight contour; 3, severe resorption, with loss of almost one third of root length; and 4, extreme resorption, with loss of more than one third of the root length.

**4. *Anterior teeth torque:*** will be accessed by the principle investigator via CBCT taken before and after the completion of retraction. The principal investigator will identify the landmarks, reference lines and planes, then will interpret the measurements in degrees.

**5. *Anterior teeth extrusion/intrusion:*** will be accessed by the principle investigator via CBCT taken before and after the completion of retraction. The principal investigator will identify the landmarks, reference lines and planes, then will interpret the measurements in millimeters.

**6. *Anterior teeth tip:*** will be accessed by the principle investigator via scanned digital models taken before and after the completion of retraction.

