**7. *Molar Rotation:*** will be accessed by the principal investigator via digitalized dental models. These records will be taken before and after the completion of retraction by identifying the landmarks, reference lines and planes, then will interpret the measurements of the angles in degrees.

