## **C] Statistical Analysis:**

- The principle investigator will be responsible for the extraction of the required data from the CBCT taken before and after retraction as well as the study models taken at every follow up visit. The data will be sent to a specialized statistician.
- The specialized statistician will be responsible for the statistical analysis of the study by:
  1. Presenting the data as mean, standard deviation (SD) and Standard error (SE) values.
  2. Using Paired t-test to compare between the friction and the frictionless group of retraction as well as to compare between the pre-and post -treatment data for each group.
  3. Using Anova test to determine the rate of anterior segment retraction.
  4. Statistically evaluate the patient acceptance for both techniques.
- For this study, the specialized statistician will use IBM11 SPSS12 Statistics Version 20 for Windows to perform the required statistics.
- The significance level will be  $P \leq 0.05$ . Highly significant variables are detected when P value is less than 0.01.

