### **Assessors Reliability:**

- To achieve high reliability for measurements, the supervisor will choose a well-experienced inter-examiner during the study.
- A training session will be provided for the examiners to ensure standard measurements techniques.
- Each examiner will complete the measurements on a model and will repeat the procedure after one week to assess the intra- and inter-examiner reliability.
- The supervisor will compare the measurements of the two assessors for disagreement with a difference of more than one millimeter.
- the supervisor will evaluate the amount of variation in measurements among and between examiners to test the performance of each assessor.
- The examiner with less reliability will receive additional training but will be replaced during the study.
- The specialized statistician will calibrate the intra and inter-examiner reliability for the measurements of the study by the Intra-class correlation coefficient (ICC). The closer the ICC to 1.0, the higher reliability between assessors. According to Fleiss:" ICC values between 0.7 and 0.9 represent good reliability.". The kappa scores between study examiners will be calculated, a range of 0.60-0.80 will represent acceptable reliability.

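### Section III has the principal investigator, who allocates the patients, read the primary outcome, although section II-D promises two blinded independent assessors

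*Protocol*

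**What the plan says.** Section II-D (Blinding) describes a single-blind trial in which the outcome assessors alone are blind. Patient names are to be hidden on the radiographs and models, and "Then two assessors will carry out, blindly and Independently, the measurements and analysis of the study". The Assessors Reliability section also assumes two readers: "The supervisor will compare the measurements of the two assessors for disagreement with a difference of more than one millimeter".

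Section III-A (Data collection methods) names someone else. Anchorage loss, the primary outcome, "will be accessed by the principal investigator via CBCT taken before and after the completion of retraction". The same sentence has that person identify the landmarks and planes and interpret the readings. Root resorption, torque, vertical position and tip are assigned in the same terms. For retraction rate, "the principle investigator will take study models for every participant monthly during the follow up visits" and then digitises and landmarks them. Molar rotation "will be accessed by the principal investigator via digitalized dental models". Section III-C (Statistical Analysis) agrees with III-A: "The principle investigator will be responsible for the extraction of the required data from the CBCT taken before and after retraction".

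On what this person knows, the Participant timeline (I-E) states: "The principle investigator will randomly allocate the patients to one of the intervention groups". It also has the principal investigator take the T0 and T1 records.

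**The concern.** The protocol gives two different answers to the question of who reads the primary outcome, and under one of them the reader knows the treatment arm. Patients and operators are not blinded, so the assessors' blinding is the trial's only protection against biased measurement.

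Placing landmarks on CBCT involves judgement. A reader who knows or recalls the arm can shift readings slightly in one direction, and the analysis cannot tell that shift from a treatment effect. The one numerical disagreement limit in the Assessors Reliability section is 1 mm, so smaller shifts between readers would not be flagged by it.

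**Working it through.** **Step 1. Who measures what.** Section III-A lists eight outcomes.

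| Outcome | Reader named in III-A |
|---|---|
| Anchorage loss (primary) | Principal investigator |
| Retraction rate | Principal investigator |
| Pain | Patient (questionnaire) |
| Root resorption | Principal investigator |
| Anterior torque | Principal investigator |
| Anterior extrusion/intrusion | Principal investigator |
| Anterior tip | Principal investigator |
| Molar rotation | Principal investigator |

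The investigator reads 7 of 8: the primary outcome and 6 of the 7 secondary ones. II-D gives all measurements to two blinded assessors. No section says that the investigator is one of the two, is excluded from reading, or is masked while reading.

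**Step 2. Does the investigator know the arm?** I-E has the investigator allocate the patients (item 5) and take T0 and T1 records (items 8 and 11). III-A has the investigator take models at the monthly visits, which are also the visits at which the T-loop is reactivated or the power chain replaced (Follow up visits). The arm is therefore known. This does not require the investigator to be the unblinded principal operator of II-D. That identity is likely from the shared tasks, but the protocol does not state it.

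**Step 3. The plan's own sample size.** Inputs from I-F: difference 1.0, SD 0.76, alpha 0.05 (taken as two-sided), power 0.8.
- Normal approximation: n = 2 × (1.960 + 0.842)² × 0.76² / 1.0² = 9.07, rounded up to 10 per group, as stated.
- Noncentral t: n = 10.12; power 79.5% at 10 per group and 93.5% at 15.

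The figure reproduces, and changing the reader does not alter it.

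**Step 4. Illustration of what a biased reader could do.** Assumptions, none given by the protocol: no true difference; SD 0.76 is in mm of anchorage loss (I-F names neither measurement nor unit); the whole shift b reaches the analysed value; two-sided independent-groups t-test, the design assumed in I-F.

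Standard error = 0.76 × √(2/n); noncentrality = b / standard error; the false-positive rate is the probability that a noncentral t with 2n − 2 degrees of freedom falls outside the central 95% limits.
- n = 10: standard error 0.340, critical value 2.101 (18 df)
- n = 15: standard error 0.278, critical value 2.048 (28 df)

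Example, b = 0.5 and n = 15: noncentrality 0.5 / 0.2775 = 1.80, rate 41.3%.

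| Shift b (mm) | 10 per arm | 15 per arm |
|---|---|---|
| 0 | 5.0% | 5.0% |
| 0.05 | 5.2% | 5.3% |
| 0.1 | 5.9% | 6.4% |
| 0.2 | 8.6% | 10.7% |
| 0.3 | 13.3% | 18.1% |
| 0.5 | 28.6% | 41.3% |

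A simulation of 200,000 runs agrees: for 0.05, 0.2 and 0.5 mm it gives 5.2, 8.6 and 28.4% (n = 10) and 5.3, 10.8 and 41.2% (n = 15).

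Sensitivity to the SD at n = 15 and b = 0.5: 59.6% if the SD is 0.6, 26.2% if it is 1.0. In SD units the range of b runs from 0.05/0.76 = 0.07 to 0.5/0.76 = 0.66, so the same rates apply to an angular reading shifted by those amounts.

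**The case against.** The strongest reply is that II-D is the section that governs blinding and its intent is clear: names hidden, two readers, independent readings. The Assessors Reliability section backs this with training, repeat readings, ICC and kappa. On that view section III is loosely worded, and making the investigator responsible for extraction could mean only delivering the data. This reading is possible for III-C. It does not fit III-A, which describes finding landmarks and interpreting readings, and that is the measurement itself. If the investigator is one of the two assessors, one of the supposedly blind readers knows the arm. Hidden names, and the coded IDs introduced for confidentiality in section V-D, do not reliably mask about 30 patients from someone who allocated and followed them.

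Second, allocation is spread over several people: the supervisor generates the sequence, an employee opens the box and the patient draws an envelope (II-A to II-C). That is correct, and the concern is not that the investigator controls the sequence. Carrying out the assignment still reveals the arm. The line "The principle investigator will continue the normal treatment and achieve proper finishing for every patient after the end of the study" adds little, because it refers to the time after the study.

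Third, the 1 mm limit is not the only reliability check; the supervisor also reviews variation within and between examiners without a threshold. This is fair. Those checks address agreement between readers, however, and are not set up to find a shift that differs by arm.

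Fourth, the false-positive rates depend entirely on the assumed shift. This stands. If the investigator were one of two readers and the readings were averaged, a 0.5 mm shift would become 0.25 mm, and the rates would be 10.7% (n = 10) and 14.0% (n = 15). Also, III-C names a paired t-test for the comparison between groups, whereas the illustration uses the independent-groups test that I-F assumes.

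**Conclusion.** The concern holds. Sections II-D and III contradict each other on who reads the primary outcome and six of the seven secondary outcomes. If section III is followed as written, the trial's only blinding is lost for 7 of its 8 outcomes. This follows from the text alone and needs no numerical assumption.

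The size of any resulting bias is unknown. Under the stated assumptions, shifts up to 0.1 mm are nearly harmless (at most 6.4%), 0.2 mm about doubles the nominal 5% at 15 per arm, and 0.5 mm gives 28.6 to 41.3%. These figures show sensitivity and do not predict what will happen. The point must be settled before any outcome is read, because readings made with knowledge of the arm can only be replaced by a complete re-reading.

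**What to change.** In section III-A (primary outcome and every CBCT or model measurement) and in III-C, replace the principal investigator as reader with the two blinded assessors of II-D. The investigator may still take the records. Add a sentence that nobody who allocates or treats patients reads outcomes, and bring I-E, II-D and Assessors Reliability into line with it.

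Useful but secondary: give the assessors files under the coded IDs in random order, state how the two readings are combined (for example, their mean), and state how any hardware on the T1 records that reveals the arm is kept from the assessors. The sponsor can choose the means, and these details could sit in a reading manual or analysis plan.

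The cost is mainly protocol wording, and the sample size is unchanged. The investigator hands over the readings. If the investigator was meant to be one of the two assessors, one more trained reader who takes no part in allocation or treatment is needed.
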